**Table 14.3.2.2**  
**Abnormal Laboratory Results by DAIDS Toxicity Grade [1] and Route of Administration**  
**Safety Population - IM HIV Uninfected Group**

Test/Route of Administration [2]	IM HIV Uninfected (N=XX)				
	Grade 0 n (%)	Grade 1 n (%)	Grade 2 n (%)	Grade 3 n (%)	Grade 4 n (%)
Analyte 1					
IV Infusion (Day 1 - Day 29)	n (xx.x%)	n (xx.x%)	n (xx.x%)	n (xx.x%)	n (xx.x%)
IM Injection (Day 30 - Day 85)	n (xx.x%)	n (xx.x%)	n (xx.x%)	n (xx.x%)	n (xx.x%)
Follow-up (Day 86 - Day 99)	n (xx.x%)	n (xx.x%)	n (xx.x%)	n (xx.x%)	n (xx.x%)
Analyte 2					
IV Infusion (Day 1 - Day 29)	n (xx.x%)	n (xx.x%)	n (xx.x%)	n (xx.x%)	n (xx.x%)
IM Injection (Day 30 - Day 85)	n (xx.x%)	n (xx.x%)	n (xx.x%)	n (xx.x%)	n (xx.x%)
Follow-up (Day 86 - Day 99)	n (xx.x%)	n (xx.x%)	n (xx.x%)	n (xx.x%)	n (xx.x%)

N= All Subjects enrolled (displayed according to assigned treatment) and denominator for percentage calculations.

[1] If a subject reported more than one abnormal result for a given analyte at any point during the study, only the result with the highest grade is counted.

[2] Indicates the route of administration by which the subject was receiving study drug at the time the laboratory result was recorded. The pre-steady state period is not included.

*Note to programmer: 1) Use TRTA to create the rows within each analyte. 2) For each value of PARAMCD select the highest grade for each subject, regardless of visit or period. 3) Count the frequency by analyte, period, and grade.*  
*Only include analytes with abnormal results in the data in this table.*

**Table 14.3.2.3.1**  
**Hematology – Clinical Laboratory Assessments and Changes from Baseline**  
**Safety Population**  
**Hemoglobin (gm/dL)**

		IM HIV Infected (N=XX)	IM HIV Uninfected (N=XX)	Total (N=XX)
Baseline [1]	N	XX	XX	XX
	Mean (SD)	XX.X (XX.XX)	XX.X (XX.XX)	XX.X (XX.XX)
	Median	XX.X	XX.X	XX.X
	25%-75%	XX – XX	XX – XX	XX – XX
	Min-Max	XX – XX	XX – XX	XX – XX
Day 15	N	XX	XX	XX
	Mean (SD)	XX.X (XX.XX)	XX.X (XX.XX)	XX.X (XX.XX)
	Median	XX.X	XX.X	XX.X
	25%-75%	XX – XX	XX – XX	XX – XX
	Min-Max	XX – XX	XX – XX	XX – XX
Change from Baseline	N	XX	XX	XX
	Mean (SD)	XX.X (XX.XX)	XX.X (XX.XX)	XX.X (XX.XX)
	Median	XX.X	XX.X	XX.X
	25%-75%	XX – XX	XX – XX	XX – XX
	Min-Max	XX – XX	XX – XX	XX – XX
Day 29	N	XX	XX	XX
	Mean (SD)	XX.X (XX.XX)	XX.X (XX.XX)	XX.X (XX.XX)
	Median	XX.X	XX.X	XX.X
	25%-75%	XX – XX	XX – XX	XX – XX
	Min-Max	XX – XX	XX – XX	XX – XX
...				
End of Study [2]				
...				
Change from Baseline				

N = All subjects in the Safety Population, and denominator for percentage calculations.

[1] Baseline is the last analyte value recorded prior to the first dose administration.

[2] End of Study is Day 85 for subjects in the IM Group.

**Note to Programmer:**

1) This table will show all scheduled visits and will be repeated for each continuous Hematology parameter listed in the SAP. Increment the last digit of the table number for each additional analyte.

2) At any visit subjects can only be on one of the dose administrations, so only one column will have results, and therefore there is no need for a total column.

Westat (Created on DDMMYYYY)  
S:\TMB302\ DA\_IM \SAS\t\_labhem1

**Table 14.3.2.4.1**  
**Chemistry - Clinical Laboratory Assessments and Changes from Baseline**  
**Safety Population**  
**BUN (mg/dL)**

*Note to programmer: Repeat Tables above for CHEMISTRY analytes, incrementing x for each new analyte.*

Westat (Created on DDMMYYYY)  
S:\TMB302\ DA\_IM \SAS\t\_labchem1

**Table 14.3.2.5.1**  
**CD4+ T-Cell Counts (cells/mm^3) and Changes from Baseline**  
**Safety Population**

[figure not shown]
		IM HIV Infected (N=XX)	IM HIV Uninfected (N=XX)	Total (N=XX)
Baseline [1]	N	XX	XX	XX
	Mean (SD)	XX.X (XX.XX)	XX.X (XX.XX)	XX.X (XX.XX)
	Median	XX.X	XX.X	XX.X
	25%-75%	XX - XX	XX - XX	XX - XX
	Min-Max	XX - XX	XX - XX	XX - XX
Day 15	N	XX	XX	XX
	Mean (SD)	XX.X (XX.XX)	XX.X (XX.XX)	XX.X (XX.XX)
	Median	XX.X	XX.X	XX.X
	25%-75%	XX - XX	XX - XX	XX - XX
	Min-Max	XX - XX	XX - XX	XX - XX
Change from Baseline	N	XX	XX	XX
	Mean (SD)	XX.X (XX.XX)	XX.X (XX.XX)	XX.X (XX.XX)
	Median	XX.X	XX.X	XX.X
	25%-75%	XX - XX	XX - XX	XX - XX
	Min-Max	XX - XX	XX - XX	XX - XX
Day 29	N	XX	XX	XX
	Mean (SD)	XX.X (XX.XX)	XX.X (XX.XX)	XX.X (XX.XX)
	Median	XX.X	XX.X	XX.X
	25%-75%	XX - XX	XX - XX	XX - XX
	Min-Max	XX - XX	XX - XX	XX - XX
...				
End of Study [2]				
...				
Change from Baseline				

N = All subjects in the Safety Population, and denominator for percentage calculations.

[1] Baseline is the last analyte value recorded prior to the first dose administration.

[2] End of Study is Day 85 for subjects in the IM Group.

[figure not shown]
Graph 14.3.2.5.4  
Mean (+/- SE) CD4+ T-Cell Counts (cells/mm^3)  
Safety Population

[1] Baseline is the last analyte value recorded on Day 1, prior to the first dose administration. When Screening is the only value, it becomes Baseline and is counted in the Baseline row and not in the Screening row.

[2] End of Study is Day 85 for subjects in the IM HIV Infected Group.

Graph 14.3.2.5.5  
Mean (+/- SE) Change from Baseline CD4+ T-Cell Counts (cells/mm^3)  
Safety Population

#subjects

[1] Baseline is the last analyte value recorded on Day 1, prior to the first dose administration. When Screening is the only value, it becomes Baseline and is counted in the Baseline row and not in the Screening row.

[2] End of Study is Day 85 for subjects in the IM HIV Infected Group.

**Table 14.3.3.1**  
**Vital Signs and Changes from Baseline**  
**Safety Population**  
**Weight (kg)**

*Note to programmer: Repeat above for VITAL SIGNS, incrementing x for each new VITAL SIGN (Temperature, Pulse, Respiration Rate, and Blood Pressure). Report only the visits where vital signs were collected, and change "analyte" to "vital sign" in the footnote.*

*Where collected, the pre-dose, post-dose (immediate) and post-dose (15 minutes) values will be presented for each visit. Label visits in the table like this example: Day 15 Pre, Day 15 Post, Day 15 Post 15 min.*

Westat (Created on DDMMYYYY)  
S:\TMB302\ DA\_IM \SAS\t\_vitals1

**Table 14.3.4.1**  
**Abnormal Physical Examination Findings**

**Safety Population**

		IM HIV Infected (N=XX)	IM HIV Uninfected (N=XX)	Total (N=XX)
Baseline [1]	Skin	n (xxx.x%)	n (xxx.x%)	n (xxx.x%)
	HEENT	n (xxx.x%)	n (xxx.x%)	n (xxx.x%)
	Lymph Nodes	n (xxx.x%)	n (xxx.x%)	n (xxx.x%)
	Lungs/Chest	n (xxx.x%)	n (xxx.x%)	n (xxx.x%)
	Heart	n (xxx.x%)	n (xxx.x%)	n (xxx.x%)
	Abdomen	n (xxx.x%)	n (xxx.x%)	n (xxx.x%)
	Genital/Rectal	n (xxx.x%)	n (xxx.x%)	n (xxx.x%)
	Extremities	n (xxx.x%)	n (xxx.x%)	n (xxx.x%)
	Neurological	n (xxx.x%)	n (xxx.x%)	n (xxx.x%)
Day 15	Skin	n (xxx.x%)	n (xxx.x%)	n (xxx.x%)
	HEENT	n (xxx.x%)	n (xxx.x%)	n (xxx.x%)
	Lymph Nodes	n (xxx.x%)	n (xxx.x%)	n (xxx.x%)
	Lungs/Chest	n (xxx.x%)	n (xxx.x%)	n (xxx.x%)
	Heart	n (xxx.x%)	n (xxx.x%)	n (xxx.x%)
	Abdomen	n (xxx.x%)	n (xxx.x%)	n (xxx.x%)
	Genital/Rectal	n (xxx.x%)	n (xxx.x%)	n (xxx.x%)
	Extremities	n (xxx.x%)	n (xxx.x%)	n (xxx.x%)
	Neurological	n (xxx.x%)	n (xxx.x%)	n (xxx.x%)
...				
End of Study [2]	Skin	n (xxx.x%)	n (xxx.x%)	n (xxx.x%)
	HEENT	n (xxx.x%)	n (xxx.x%)	n (xxx.x%)
	Lymph Nodes	n (xxx.x%)	n (xxx.x%)	n (xxx.x%)
	Lungs/Chest	n (xxx.x%)	n (xxx.x%)	n (xxx.x%)
	Heart	n (xxx.x%)	n (xxx.x%)	n (xxx.x%)
	Abdomen	n (xxx.x%)	n (xxx.x%)	n (xxx.x%)
	Genital/Rectal	n (xxx.x%)	n (xxx.x%)	n (xxx.x%)
	Extremities	n (xxx.x%)	n (xxx.x%)	n (xxx.x%)
	Neurological	n (xxx.x%)	n (xxx.x%)	n (xxx.x%)

N = All subjects in the Safety Population, and denominator for percentage calculations.

[1] Baseline is the last analyte value recorded, prior to the first dose administration.

[2] End of Study is Day 85 for subjects in the IM Group.

**Note to Programmer: Include all visit days that Physical Exam is recorded.**

**Table 14.3.5.1**  
**Summary of Study Drug Administration**  
**Safety Population**

		IM HIV Infected (N=XX)	IM HIV Uninfected (N=XX)	Total (N=XX)
Cumulative Dose (mg)	N	XX	XX	XX
	Mean (SD)	XX.X (XX.XX)	XX.X (XX.XX)	XX.X (XX.XX)
	Median	XX.X	XX.X	XX.X
	25%-75%	XX - XX	XX - XX	XX - XX
	Min-Max	XX - XX	XX - XX	XX - XX
Duration of Treatment (days from first dose)	N	XX	XX	XX
	Mean (SD)	XX.X (XX.XX)	XX.X (XX.XX)	XX.X (XX.XX)
	Median	XX.X	XX.X	XX.X
	25%-75%	XX - XX	XX - XX	XX - XX
	Min-Max	XX - XX	XX - XX	XX - XX

N = All subjects in the Safety Population.

**Table 14.4.1**  
**HIV Treatment Satisfaction Questionnaires**  
**Intent-to-Treat Population - HIV Infected Group**

Questions	IM HIV Infected (N=XX)				
	HIVTSQs (Day 29)		HIVTSQs (Day 85)		P-Value [1]
How satisfied are you With your current treatment?	N Mean (SD) Median 25%-75% Min-Max	XX XX.X (XX.XX) XX.X XX - XX XX - XX	XX XX.X (XX.XX) XX.X XX - XX XX - XX	xxxx	XX XX.X (XX.XX) XX.X XX - XX XX - XX
How well controlled do You feel your HIV has been recently?	N Mean (SD) Median 25%-75% Min-Max	XX XX.X (XX.XX) XX.X XX - XX XX - XX	XX XX.X (XX.XX) XX.X XX - XX XX - XX	xxxx	XX XX.X (XX.XX) XX.X XX - XX XX - XX
How satisfied are you with any side effects of your present treatment?	N Mean (SD) Median 25%-75% Min-Max	XX XX.X (XX.XX) XX.X XX - XX XX - XX	XX XX.X (XX.XX) XX.X XX - XX XX - XX	xxxx	XX XX.X (XX.XX) XX.X XX - XX XX - XX
How satisfied are you with the demands made by your current treatment	N Mean (SD) Median 25%-75% Min-Max	XX XX.X (XX.XX) XX.X XX - XX XX - XX	XX XX.X (XX.XX) XX.X XX - XX XX - XX	xxxx	XX XX.X (XX.XX) XX.X XX - XX XX - XX
...					

N = All subjects in the Intent-to-Treat Population, and denominator for percentage calculations.

[1] Wilcoxon signed rank test comparing paired change in mean response at Day 29 to Day 85.

**Table 14.4.2**  
**Study Medication Satisfaction Questionnaires**  
**Intent-to-Treat Population - HIV Uninfected Group**

Questions	IM HIV Uninfected (N=XX)			
	SMSQs (Day 29)	SMSQs (Day 85)	P-value [1]	SMSQc (Day 85)
How satisfied are you with your current study medication?	N Mean (SD) Median 25%-75% Min-Max	XX XX.X (XX.XX) XX.X XX - XX XX - XX	XX XX.X (XX.XX) XX.X XX - XX XX - XX	xxxx XX.X (XX.XX) XX.X XX - XX XX - XX
How satisfied are you with any side effects of your present study medication?	N Mean (SD) Median 25%-75% Min-Max	XX XX.X (XX.XX) XX.X XX - XX XX - XX	XX XX.X (XX.XX) XX.X XX - XX XX - XX	xxxx XX.X (XX.XX) XX.X XX - XX XX - XX
How satisfied are you with the demands made by your current study medication?	N Mean (SD) Median 25%-75% Min-Max	XX XX.X (XX.XX) XX.X XX - XX XX - XX	XX XX.X (XX.XX) XX.X XX - XX XX - XX	xxxx XX.X (XX.XX) XX.X XX - XX XX - XX
How convenient have you been finding your study Medication to be recently?	N Mean (SD) Median 25%-75% Min-Max	XX XX.X (XX.XX) XX.X XX - XX XX - XX	XX XX.X (XX.XX) XX.X XX - XX XX - XX	xxxx XX.X (XX.XX) XX.X XX - XX XX - XX
...				

N = All subjects in the Intent-to-Treat Population, and denominator for percentage calculations.

[1] Wilcoxon signed rank test comparing paired change in mean response at Day 29 to Day 85.

**Table 14.4.3**  
**Preference Assessment**  
**Intent-to-Treat Population**

	IM	IM	Total (N=XX)
	HIV Infected (N=XX)	HIV Uninfected (N=XX)	
Which type of administration do you prefer?	IV Infusion n (xxx.x%)	IM Injection n (xxx.x%)	n (xxx.x%) n (xxx.x%)

Full question text: For the past 8 weeks you have received IM injections every 2 weeks. Today we would like you to compare your experience on the IM injections with the IV infusion you received previously during this study. Which type of administration do you prefer?

N = All subjects in the Intent-to-Treat Population, and denominator for percentage calculations.

Westat (Created on DDMMYYYY)  
S:\TMB302\ DA\_IM \SAS\t\_preference

## SUPPLEMENTAL TABLES (ANALYSIS BY PERIOD)

**Table 14.3.1.1.2**  
**Treatment-Emergent Adverse Events Summary**  
**Safety Population - IM HIV Infected**  
**By Period**

	IM HIV Infected (N=XX)			
	Investigational Period		Follow-up Period	
	Initial Period 15 min IV Infusion	IM Injection	15 min IV Infusion	Total
TEAE [1]	n (xxx.x%)	n (xxx.x%)	n (xxx.x%)	n (xxx.x%)
Serious TEAE [2]	n (xxx.x%)	n (xxx.x%)	n (xxx.x%)	n (xxx.x%)
TEAE with Death Outcome	n (xxx.x%)	n (xxx.x%)	n (xxx.x%)	n (xxx.x%)
TEAE Leading to Discontinuation	n (xxx.x%)	n (xxx.x%)	n (xxx.x%)	n (xxx.x%)
TEAE Related to Study Drug [3]	n (xxx.x%)	n (xxx.x%)	n (xxx.x%)	n (xxx.x%)
Severe TEAE [4]	n (xxx.x%)	n (xxx.x%)	n (xxx.x%)	n (xxx.x%)
Class C TEAE [5]	n (xxx.x%)	n (xxx.x%)	n (xxx.x%)	n (xxx.x%)

N = All subjects in the Safety Population (displayed according to actual treatment received), and denominator for percentage calculations.

TEAE = Treatment-Emergent Adverse Event.

NOTE: Identical TEAEs are counted only once per subject.

[1] Number(%) of subjects with at least one TEAE.

[2] Number(%) of subjects with at least one serious TEAE, excluding death, as identified by the investigator.

[3] Definitely, probably, or possibly.

[4] Severity/Grade 3 or higher (severe or potentially life threatening).

[5] Per the CDC Classification System for HIV Infection.

**Table 14.3.1.1.3**  
**Treatment-Emergent Adverse Events Summary**  
**Safety Population - IM HIV Uninfected**  
**By Period**

	IM HIV Uninfected (N=XX)			
	Pre-Steady State + IV Infusions Period	Investigational IM Injection	Follow-up Period	Total
TEAE [1]	n (xxx.x%)	n (xxx.x%)	n (xxx.x%)	n (xxx.x%)
Serious TEAE [2]	n (xxx.x%)	n (xxx.x%)	n (xxx.x%)	n (xxx.x%)
TEAE with Death Outcome	n (xxx.x%)	n (xxx.x%)	n (xxx.x%)	n (xxx.x%)
TEAE Leading to Discontinuation	n (xxx.x%)	n (xxx.x%)	n (xxx.x%)	n (xxx.x%)
Suspected Adverse Reaction [3]	n (xxx.x%)	n (xxx.x%)	n (xxx.x%)	n (xxx.x%)
Severe TEAE [4]	n (xxx.x%)	n (xxx.x%)	n (xxx.x%)	n (xxx.x%)
Class C TEAE [5]	n (xxx.x%)	n (xxx.x%)	n (xxx.x%)	n (xxx.x%)

N = All subjects in the Safety Population (displayed according to actual treatment received), and denominator for percentage calculations.

TEAE = Treatment-Emergent Adverse Event.

NOTE: Identical TEAEs are counted only once per subject.

[1] Number(%) of subjects with at least one TEAE.

[2] Number(%) of subjects with at least one serious TEAE, excluding death, as identified by the investigator.

[3] Possibly related to study drug.

[4] Severity/Grade 3 or higher (severe or potentially life threatening).

[5] Per the CDC Classification System for HIV Infection.

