**For HIV-uninfected healthy volunteers:**

If 1 DLT occurs within 7 days of a subject receiving Trogarzo® by IVI or IM injection, then the DMC should be notified, and dosing of additional IM Group subjects may continue. However, the individual experiencing the DLT should discontinue dosing and be observed for 28 days prior to study discontinuation.

If 2 DLTs occur within 7 days of a subject receiving Trogarzo® by IVI or by IM injection then the DMC should be notified; however, dosing of additional HIV-1 uninfected IM Group subjects may continue. The individuals experiencing the DLT should discontinue dosing and be observed for 28 days prior to study discontinuation. The DMC should at this point review.

If 3 DLTs occur within 7 days of a subject receiving Trogarzo® by IVI or by IM injection, then the DMC should be notified, and further dosing of IM Group subjects should be suspended. All IM Group subjects should resume dosing as per current FDA-approved administration instructions.

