#### IM Group: HIV infected subjects

The HIV infected subjects in the IM Group (subject numbers XX-501 – XX-5nn where XX is the site number and nn is the last subject number) will be enrolled. Subjects will receive the first two doses of study drug in accordance with the Trogarzo® prescribing information (diluted in normal saline and administered over 15 minutes via IVI) at Day 1 and again at Day 15. The next four doses of Trogarzo® through Day 71 (10 weeks) will be administered as an IM injection. At Day 85 (12 weeks), IM Group subjects will revert to diluted IVI dosing over 15 minutes in accordance with the Trogarzo® prescribing information.

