#### IM Group: HIV uninfected subjects

The HIV uninfected subjects in the IM Group (subject numbers XX-601 – XX-6nn) will be enrolled.

**Pre-Steady State Phase:** Subjects will receive a 2000 mg infusion over 60 minutes on Day minus 55 followed by 3 doses of 800 mg infusion over 15 minutes on Days minus 41, 27, and Day minus 13. On Day 1 the subjects will enter the Study Treatment Phase.

**Study Treatment Phase:** HIV uninfected subjects in the IM Group will receive the first two doses of Trogarzo® in accordance with the prescribing information (diluted in 250 mL normal saline and administered over 15 minutes via IVI) at Day 1 and again at Day 15. The next four doses of Trogarzo® will be administered as an IM injection. HIV uninfected subjects will discontinue dosing after the Day 71 study drug administration.

All HIV infected study subjects in both Groups will be observed for 15 minutes after each study drug administration, and HIV uninfected subjects will be observed for 60 minutes. All adverse events (AEs) will be recorded. Vital signs will be measured and recorded at the beginning and end of this observation period.

For the PK profile of Trogarzo® following IM administrations, pre-dose samples will be collected at selected time points, along with samples at 2, 7, 10, and 14 days post-dose for the last two doses of study drug (via IVI), and for the last two IM injection doses for all subjects.

[figure not shown]

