#### **2.4.4. Replacement**

If a subject in the study is discontinued due to any reason other than safety as detailed in Section 4.3 (Safety Monitoring and Toxicity Management Plan) of the study protocol, another subject may be enrolled to replace the lost subject to achieve a total of 20 subjects successfully completing participation in the study.

Study participants who:

1. miss 2 consecutive visits or
2. have more than one treatment visit out of window or
3. have 3 non-treatment visits over 4 weeks that are out of window will be discontinued from the study and replaced.

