##### **3.2.2. Safety (SAF) Population**

All subjects who receive at least one partial dose of study drug will be included in the SAF Population. Subjects will be analyzed according to the treatment (dose regimen) they actually received. The SAF Population will be used for the safety analyses.

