### **3.4. Statistical Methods**

#### **3.4.1. General Overview and Plan of Analysis**

The data collected are intended primarily for clinical review and interpretation. The analysis of study data will be primarily descriptive, with emphasis on tabular and graphical displays. Descriptive statistics will be used to guide decisions as to the clinical relevance of findings. Unless otherwise stated, p-values will be determined only if they appear to be warranted from the summary statistics.

Where applicable, summaries will be displayed in the following subject groupings:

- IM HIV infected
- IM HIV uninfected
- Total

In addition, the safety and efficacy summaries will present results grouped by analysis periods, where applicable:

- IM HIV infected: Initial Period (15 min IV Infusion); Investigational Period (IM Injection); Follow-up Period (15 min IV Infusion)
- IM HIV uninfected: Pre-Steady State + IV Infusion Period; Investigational Period (IM Injection); Follow-up Period

For continuous data, descriptive statistics will be presented as number of subjects (n), mean, standard deviation, median, minimum, and maximum. For categorical data, the frequency and percentage of subjects in each category will be presented. Percentages will be based on non-missing data unless otherwise specified.

Data collected during this study will be assigned to the appropriate Analysis Phase, Analysis Period, and Analysis Sub period (where applicable) in which it occurred. The assignment will be based on the visit date, or in the case of cumulative data such as AEs and concomitant procedures, based on the start date. Tables, listings, and graphs will reflect the assignments. A complete description of the phases, periods, and sub periods for the HIV infected and HIV uninfected groups can be found in Appendix 1.

Data will be described and analyzed using the SAS System Version 9 (SAS Institute Inc., Cary, NC, SAS System). Individual subject data will be presented in subject data listings.

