**Notes Applicable to All Tables**

General Programming Notes:

1. The tables will be programmed to show aggregate data only.
2. Review the data prior to programming. Check the data for inconsistencies and anomalies. Report suspected data errors to the lead programmer who can determine if they should be addressed by DM.
3. Follow the Quality Control Plans (\\\Westat.com\dfs\CTWRKGRP\PUBLIC\Resources\DA\QC\_Plans) for Tables, Listings, and Graphs. Perform the quality checks, using the Checklist.
4. Always check the population totals. All subjects should be accounted for in all tables. A row for "Unknown" or "Missing" values can be added to any table as appropriate to account for all subjects.
5. For summary statistics: N should always be an integer; minimum and maximum should have the same number of significant digits as is present in the data; mean and median should be calculated to be one additional significant digit than the data collected; standard deviation should be calculated to be two additional significant digits than the data collected.
6. Percentages should be calculated to one decimal place. The true number of treated subjects, which appears at the top of columns in most tables should be calculated once in libnames.sas and put into macro variables to ensure consistency. This number should not be re-calculated when calculating percentages.
7. Follow the mocks, especially regarding details, such as titles, capitalization, order of columns and row labels, and footnotes. Standard table formatting may be followed, as some mocks may have been created due to space/pagination considerations. The visit names in the mocks are examples only. Consult the protocol and SAP and present all scheduled visits for the item in question.
8. Additional footnotes may be required to fully/more accurately describe the contents of a table (decided during development). Consult project leader and lead biostatistician with questions.

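### By-period AE tables in both SAPs divide every period column by the group's whole Safety Population, so subjects who leave before the new route lower its reported incidence

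*SAP*

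**What the plan says.** Both SAPs define the Safety Population in section 3.2.2 without reference to route: "All subjects who receive at least one partial dose of study drug will be included in the SAF Population". The by-period AE shells apply it separately to each group: IM HIV infected and IM HIV uninfected in the IM SAP (supplemental by-period tables, 14.3.1.x), and Sentinel, Core HIV-infected and Core HIV-uninfected in the IV push SAP (Tables 14.3.1.1.x to 14.3.1.7.x). Each shell has one N spanning the infusion, investigational and follow-up columns, and its footnote reads "N = All subjects in the Safety Population (displayed according to actual treatment received), and denominator for percentage calculations". Note 6 of the programming notes to both sets of mock tables has the number treated computed once and stored, and adds: "This number should not be re-calculated when calculating percentages". Section 3.4.1 of each SAP assigns data to periods by date, and "in the case of cumulative data such as AEs and concomitant procedures, based on the start date".

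Nobody starts on the new route. For HIV-infected IM subjects, "Subjects will receive the first two doses of study drug in accordance with the Trogarzo® prescribing information", that is, by infusion on Days 1 and 15. For uninfected IM subjects, "Subjects will receive a 2000 mg infusion over 60 minutes on Day minus 55 followed by 3 doses of 800 mg infusion", and then two more infusions on Days 1 and 15. The Core Group has the same lead-ins. Sentinel subjects pass through infusion and then the 10-, 5- and 1-minute steps before push.

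**The concern.** A subject who stops during the infusion lead-in, or a Sentinel subject who stops at an earlier step, was never at risk of an event on IM or push but is counted as if at risk in that column. The infusion column has the right denominator, because everyone in the Safety Population had an infusion first. Only the later columns are diluted.

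The plan foresees such losses. Missed or out-of-window visits lead to discontinuation. Under Protocol section 4.3, an uninfected IM Group volunteer with a dose-limiting toxicity on infusion or IM leaves treatment: "However, the individual experiencing the DLT should discontinue dosing and be observed for 28 days prior to study discontinuation". A Sentinel subject with such a toxicity leaves the study. SAP section 2.4.4 says that for non-safety losses "another subject may be enrolled to replace the lost subject to achieve a total of 20 subjects successfully completing participation in the study", so the lost subject and the replacement can both be in N.

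Safety of IM and push is a primary objective. The overall IM AE tables mix lead-in and IM events, so the by-period tables are the AE tables that isolate the new route. In the IV push SAP the main AE summaries are themselves by period.

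**Working it through.** The documents state no AE rate, lead-in loss or per-period N, so there is no planned figure to reproduce. The 20 per route in Protocol section 9.8 concerns PK power and is not an input.

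**Inputs**
- m: subjects in the table's group with at least one dose by the column's route. The split by HIV status is not given; m=10 is assumed.
- k: subjects in the same group's Safety Population who left before that route. Not given; 1 to 4 is assumed.
- x: subjects with an event starting in that period; x=3 is assumed.
- Sentinel Group size: 5 (Protocol section 3.1).

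**Formulas**
- Percentage as planned: x/(m+k)
- Percentage among those exposed: x/m
- Ratio of the two: m/(m+k)

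The ratio does not depend on x. It assumes that no early leaver contributes an event to the later column.

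**One IM or Core group, m=10, x=3**

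| k | m/(m+k) | As planned | Among exposed |
|---|---|---|---|
| 0 | 10/10 = 1.00 | 3/10 = 30.0% | 30.0% |
| 1 | 10/11 = 0.91 | 3/11 = 27.3% | 30.0% |
| 2 | 10/12 = 0.83 | 3/12 = 25.0% | 30.0% |
| 3 | 10/13 = 0.77 | 3/13 = 23.1% | 30.0% |
| 4 | 10/14 = 0.71 | 3/14 = 21.4% | 30.0% |

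**Sentinel Group.** If one of the five is lost before push and not replaced, m=4 and k=1. One subject with an event on push shows as 1/5 = 20% instead of 1/4 = 25%, a factor of 0.80. So the dilution does not require replacement; replacement only determines whether N grows.

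**Re-enrolled subjects.** The IM SAP Addendum presents only the second enrollment for all data other than PK. An HIV-infected IM subject who is discontinued in the lead-in and re-enrolls is therefore not counted a second time through the abandoned first enrollment, and adds nothing to k.

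**The case against.** The shells might already imply a per-route N, since the footnote speaks of display by actual treatment and section 3.2.2 calls for analysis as treated. That does not hold: the same footnote phrase appears in IM Table 14.3.1.1.1, which has no period columns, and the by-period shells show a single N. The general rule that percentages rest on non-missing data applies only where nothing else is specified, and here the footnote specifies otherwise. Note 6 may be meant only for consistency, and it speaks of most tables, but nothing exempts these.

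Other objections stand and limit the point:
- The effect is zero if nobody leaves early, and the documents give no loss rate.
- The IM by-period tables are headed supplemental, the analysis is primarily descriptive, and each cell prints a count beside its percentage. The dosing, discontinuation and AE listings would let a reader count those exposed by hand.
- The period diagrams in Appendix 1 cannot be seen in the copy reviewed. Which column receives a late event from a leaver still under 28-day observation cannot be confirmed.

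A reader might also infer more than the documents support:
- *A factor of 20/(20+k), or a distorted upper confidence limit.* No by-period AE table pools 20 subjects; they are split by HIV status or by Sentinel and Core. No AE shell prints a confidence limit.
- *A denominator of everyone who ever received the drug.* It is one group within one portion, and the IM SAP treats the IM and push portions as separate studies.
- *Replacement makes the dilution systematic.* Replacement is optional in the sentence quoted above and in the protocol; only the SAP's visit-adherence rule states it outright. It also covers subjects lost after receiving the new route, who belong in the denominator.
- *The comparison with infusion always favours the new route.* Period lengths differ. At 14 days per dose, HIV-infected IM subjects have 2 × 14 = 28 days on infusion against 4 × 14 = 56 on IM, and uninfected subjects have 6 × 14 = 84 against 56. The net direction of the crude contrast is not set by the denominator alone.

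**Conclusion.** The point holds. Followed as written, the by-period AE shells of both SAPs give too low a percentage in the IM, push and later Sentinel columns whenever anyone in that group leaves before the route concerned. The denominator error is always downward for the later route, by the factor m/(m+k). The sizes shown (0.91 to 0.71 for an assumed m=10 with 1 to 4 early losses, and 0.80 for one early loss among five Sentinel subjects) rest on assumed loss numbers, and with no early losses there is no error.

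This is a should-fix. It would be tempting to call it a threat to the primary safety conclusion. The documents do not support that: counts are shown, no test of AE rates is planned, and exposure can be recovered from the listings.

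**What to change.** In the by-period AE shells of both SAPs:
- Print under each period column n, the number of Safety Population subjects in that group with at least one (partial) dose by that column's route or Sentinel step. For Follow-up, print the number who entered it.
- Use that n as the column's percentage denominator and amend the footnote accordingly.
- Keep the group N for the Total column.
- State that note 6 does not apply to these period columns.

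The cost is one derived count per period, with no new data. If there are early losses, the new-route percentages become slightly less favourable; if there are none, nothing changes. The fix does not address the unequal period lengths, so a crude comparison of the new-route and infusion columns still needs that caution.
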